2.1 Definitions for subjects and treatments

2.1.1 Analysis sets

Full Analysis Set (FAS) comprises all patients who received at least one dose of study medication.

Safety Set includes all patients who received at least one dose of study medication.

Note that the patient population for both FAS and Safety Set are the same.

Dose-determining Set (DDS) consists of all patients from the Safety Set who either (i) meet the minimum exposure criteria and have sufficient safety evaluations as defined below, or (ii) experience a DLT. The patients in the DDS enrolled in the dose-finding part of the study will be the patients used for determination of the MSSD.

Note: this is a clarification to the definition of the DDS in Section 9.1.3 of the protocol. The DDS contains all patients who experienced a DLT regardless of whether they permanently discontinued treatment as Section 5.1.2.8 defines circumstances where patients who experienced a DLT can resume treatment.

A patient is considered to have met the minimum exposure criteria and to have had sufficient safety evaluations if they have not missed > 20% of the planned doses and no more than 6 consecutive doses in the first 28 days, and have completed all required safety evaluations through Study Day 28.

Patients in the DDS will be identified based on the list of evaluable patients used for determination of the MSSD, as well as the VAP M3 Protocol Deviations. Patients with protocol deviation code 18 (indicating exclusion from dose-finding population) will be excluded from DDS.

Patients will be analyzed by stratum and for each stratum, patients will be categorized according to the first dose level they received. Patients will be categorized the following way: (1) Group 1, including patients with starting dose of 5mg AM + 5mg PM or 5mg AM + 10mg PM; (2) Group 2, including patients with starting dose of 10mg AM + 10mg PM; (3) Group 3, including patients with starting dose of 10mg AM + 15mg PM or 15mg AM + 15mg PM. Such categorization depends on the highest dose level being reached in each stratum. For example, the highest dose level reached in Stratum 2 is 10mg AM + 10mg PM, so there will be only two groups for Stratum 2: (1) Group 1, including patients with starting dose of 5mg AM + 5mg PM or 5mg AM + 10mg PM; (2) Group 2, including patients with starting dose of 10mg AM + 10mg PM.

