## **9.1 Analysis sets**

In general, data summaries will be presented by dose levels unless otherwise stated. Dose levels may be combined for summary purposes based on the observed outcomes. For example, it may be prudent to summarize according to starting dose received as: lower than MSSD, MSSD, and higher than MSSD. DLT outcomes will be summarized separately by dose level and stratum. Additional key safety information, such as incidence of hematologic adverse events and labs, may be summarized separately by stratum.

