2.2.2 Study treatment

Study treatment data will be summarized descriptively by stratum and group using the Safety Set.

The duration of exposure will be summarized by length of exposure, as well as by duration category (none, < 4 weeks, 4 – < 8 weeks, 8 – < 12 weeks, 12 – < 16 weeks, 16 – < 20 weeks, 20 – < 24 weeks, 24 – < 36 weeks, 36 – < 48 weeks, 48 – < 60 weeks etc).

The following algorithm will be used to calculate the duration of study treatment exposure.

Duration of exposure (days) = [(date of last administration of study treatment) – (date of first administration of study treatment) + 1].

The duration includes the periods of temporary interruption.

Study dose

Cumulative dose is defined as the total dose given during the study treatment exposure. For patients who did not take any drug, the cumulative dose is by definition equal to zero. The total dose taken will be calculated based on INC424 DOSE eCRF page. Dose intensity (DI) is defined as:

$$DI \text{ (mg/day)} = \text{Cumulative dose (mg)} / \text{Duration of exposure (days)}$$

Relative dose intensity (RDI) for the first cycle of treatment is defined as:

$$RDI \text{ (\%)} = (\text{Cumulative dose over first cycle}) / (\text{Total planned starting dose over first cycle}) \times 100\%$$

where total planned starting dose as Duration of treatment (days) * starting dose of the assigned cohort.

The summaries of cumulative dose, DI and RDI will be presented.

A dose reduction is defined as a reduction of the total daily dose to a non-zero dose of one day or greater. A dose interruption is defined as a total daily dose of 0 mg for a duration of one day or greater.

The number (%) of subjects who had a dose interruption or dose reduction will also be summarized.

The dosing information will be listed by stratum, dose level and patient.

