2.3 Safety evaluation

For all safety analyses, the Safety Set will be used, except for summaries of DLTs, which will be presented for the DDS. All listings will be presented by dose levels and all tables will be presented by groups of dose levels in the Safety Set.

The overall observation period will be divided into three mutually exclusive segments:

1. pre-treatment period: from day of patient's informed consent to the day before first dose of study medication
2. on-treatment period: from day of first dose of study medication to 30 days after last dose of study medication
3. post-treatment period: starting at day 31 after last dose of study medication.

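### SAP reporting Group 3 pools Stratum 1 starters at 15 mg BID, the declared MSSD, with 10/15 mg starters in the AE, exposure and dose-reduction tables

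*SAP*

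**What the plan says.** SAP 2.1.1 sets the general rule: "Patients will be analyzed by stratum and for each stratum, patients will be categorized according to the first dose level they received". It then forms three reporting groups. Group 1 holds the two lowest starting doses and Group 2 holds 10 mg BID alone. The third is "Group 3, including patients with starting dose of 10mg AM + 15mg PM or 15mg AM + 15mg PM". The table in SAP 2.1.3 repeats this by assigning both S1D4 and S1D5 to Group 3.

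For dosing, SAP 2.2.2 states: "Study treatment data will be summarized descriptively by stratum and group using the Safety Set". In the same section, "The number (%) of subjects who had a dose interruption or dose reduction will also be summarized", while the patient-level data are kept at full resolution: "The dosing information will be listed by stratum, dose level and patient". For safety, SAP 2.3 states: "All listings will be presented by dose levels and all tables will be presented by groups of dose levels in the Safety Set".

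Protocol 9.1 makes dose level the default display and allows exceptions: "Dose levels may be combined for summary purposes based on the observed outcomes". Its example is that "it may be prudent to summarize according to starting dose received as: lower than MSSD, MSSD, and higher than MSSD". Protocol 9.5.2.1 likewise lets safety tables use dose levels or groups of them, depending on how many levels and patients there are.

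**The concern.** The Amendment 4 rationale says that 15 mg BID was declared the Stratum 1 MSSD on first-cycle DLTs. It adds that patients who started there then had frequent dose reductions after the first cycle, and for that reason the expansion starting dose was changed. The informative period for 15 mg BID is therefore after Day 28. For that period the SAP's AE and dosing tables show 15 mg BID only mixed with 10/15 mg.

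The scheme is also uneven. Group 2 gives 10 mg BID its own column in both strata, which covers the Stratum 2 MSSD and the Amendment 4 starting dose in Stratum 1. The declared Stratum 1 MSSD is the only one of these doses without a column. A reader of the report tables could not see its rate of later dose reductions or AEs without rebuilding it from the listings.

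**Working it through.** **1. The plan's own count.** Protocol 9.8 and SAP 2.6 give at least 3 patients per dose level, 5 levels, at least 9 at the MSSD, 10 expansion patients per stratum, about 20 at 10 mg BID in Stratum 1, and a DDS of about 72.
- Dose finding per stratum: 4 × 3 + 9 = 21, as stated. Two strata: 42.
- Expansion: 10 (Stratum 2) + 3 (Stratum 1, already at 15 mg BID) + (20 − 3) = 30, assuming 3 were already at 10 mg BID.
- Total: 42 + 30 = 72, which matches. The documents do not show their own breakdown; 42 + 20 + 10 also gives 72.

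The point changes no sample size.

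**2. Make-up of Group 3 in Stratum 1.** Inputs are from the Amendment 4 rationale: 24 patients in dose escalation, of whom 9 were at 15 mg BID, and 3 in expansion at 15 mg BID. No Stratum 1 expansion patients were added by 28 July 2015.
- 15 mg BID starters: 9 + 3 = 12.
- Patients on the four lower levels: 24 − 9 = 15.
- The 10/15 mg count is not stated. Assume at least 3 per level (Protocol 5.1.2.4 asks for at least 3 evaluable patients per level). The count then lies between 3 and 15 − 3 × 3 = 6.
- Group 3 total: 12 + 3 = 15 to 12 + 6 = 18.
- Share not starting at the MSSD: 3/15 = 20% to 6/18 = 33%.

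**3. Which SAP tables separate 15 mg BID.** Stratum 2 went no higher than 10 mg BID (SAP 2.1.1), so any display by dose level isolates Stratum 1 15 mg BID.

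| Output | SAP section | Display | Period |
|---|---|---|---|
| DLT incidence | 2.3.2 | dose level | to Day 28 |
| BLRM posterior DLT probabilities | 2.3.1 | dose and stratum | to Day 28 |
| Compliance (relative dose intensity) | 2.2.5 | dose level | first cycle |
| Exposure, dose intensity, interruptions and reductions | 2.2.2 | stratum and group | whole treatment, except first-cycle relative dose intensity |
| AE tables | 2.3, 2.3.2 | groups of dose levels | on-treatment period |

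Medical history (SAP 2.2.1) is also by dose, but it is baseline data. SAP section 2 says core and extension data are summarized together, so the grouped tables carry the follow-up beyond Day 28.

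**4. SAP against protocol section 9.** SAP section 2 says the analysis follows protocol section 9. There, 9.3 summarizes dose, duration and daily dose by dose level. Section 9.5.2.2 includes dose level among the breakdowns of AE incidence. Section 9.5.2.3 summarizes time to onset of grade 3 or higher safety event categories by dose level. SAP 2.2.2 and 2.3 use groups for exposure and for all safety tables, and the SAP does not mention the time-to-onset output. The two documents do not say which display governs.

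**The case against.** **Grouping is permitted.** Protocol 9.1 and 9.5.2.1 allow it, and the 9.1 example is only a suggestion. Taken literally in Stratum 1, where the MSSD is the top level, that example would pool 10 mg BID with the other lower doses and hide the dose that Amendment 4 set out to evaluate. This stands. A reader might infer a protocol breach, but the documents do not support that. It is also why Group 2 should be kept.

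**The SAP already isolates the dose now of interest.** New Stratum 1 patients start at 10 mg BID after Amendment 4, and the later reductions at 15 mg BID were already seen at the interim analysis. This lowers the stakes. It does not explain why the final tables should mix the declared MSSD with another level.

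**Nothing is lost.** Dosing and safety listings are by dose level, so the 15 mg BID results can be rebuilt by hand. This stands.

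**It may not be true that no table after Day 28 isolates 15 mg BID.** A reader might infer that from the SAP alone. Protocol 9.3, 9.5.2.2 and 9.5.2.3 have wording by dose level, the table shells are not among the documents, and the exploratory section is redacted. What can be said is that the SAP's own specification does not provide such a table and conflicts with the protocol wording.

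**Laboratory and spleen outputs.** SAP 2.3.3 and the efficacy text describe most of these by stratum and give no grouping for the 50% spleen response. A reader might conclude that starting dose is missing from them. However, the rules in SAP 2.1.1 and 2.3 may already imply dose groups, and protocol 9.1 allows laboratory data by stratum. This is unclear wording only.

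**Conclusion.** The point holds as a low-cost improvement to the reporting plan. In the SAP's AE, exposure, dose-intensity and dose-reduction tables, the declared Stratum 1 MSSD is pooled with 10/15 mg, and the SAP's outcome tables by dose level end at Day 28. About 20% to 33% of Group 3 did not start at the MSSD.

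That share rests on two things: at least 3 patients at each lower level, and counts as of July 2015. The change to 10 mg BID took effect only on approval of Amendment 4, so later 15 mg BID starters are not excluded.

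A reader might go on to infer a bias of known size. The documents do not allow it. They give no later-reduction rate by starting dose, and the prior DLT probabilities in protocol Table 9-1 concern the first cycle, which the SAP already reports by dose level. Any bound from the group sizes alone limits what the table reveals and is not evidence of distortion.

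**What to change.** In SAP 2.1.1 and 2.1.3, give Stratum 1 15 mg BID (S1D5) its own reporting column in the AE, exposure/dose-intensity and dose-interruption/reduction tables. Keep Group 2 (10 mg BID) unchanged.

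Reconcile SAP 2.2.2 and 2.3 with protocol 9.3, 9.5.2.2 and 9.5.2.3 by stating which outputs are by dose level and which are by group. Say also whether time to onset of grade 3 or higher safety event categories is still planned.

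As an editorial clarification, state the grouping of each laboratory and spleen output.

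The cost is SAP wording and programming. No dose, enrolment or data collection changes. The downside is a separate 10/15 mg column of about 3 to 6 patients, whose percentages will be imprecise.

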2.1.2 Study day

The study day is calculated as:

For assessments starting on or after the start date of study treatment:

Study day = date of examination – start date of study drug + 1.

For assessments starting before the start date of study treatment:

Study day = date of examination – start date of study drug.

2.1.3 Treatments

During the study all patients will receive INC424 tablets. INC424 tablets will be the only investigational drug in this study.

The following notation will be used for the dose levels by stratum:

Daily dose regimens Morning dose + evening dose	Dose levels	Dose levels for stratum 1	Dose levels for stratum 2	Reporting for stratum 1	Reporting for stratum 2
5mg AM + 5mg PM	1	S1D1	S2D1	Group 1	Group 1
5mg AM + 10mg PM	2	S1D2	S2D2	Group 1	Group 1
10mg AM + 10mg PM	3	S1D3	S2D3	Group 2	Group 2
10mg AM + 15mg PM	4	S1D4	S2D4	Group 3	Group 3
15mg AM + 15mg PM	5	S1D5	S2D5	Group 3	Group 3

Baseline for efficacy and safety assessments is defined as last assessment prior to or on the first INC dose date unless there is a separate definition provided [REDACTED].

2.2 Subjects and treatments

2.2.1 Demographics and other baseline characteristics

Demographic characteristics will include age, age group (<65, >=65), sex, race, ethnicity, Body Mass Index (BMI) and Eastern Cooperative Oncology Group (ECOG) status at baseline. BMI [kg/m²] = weight[kg] / (height[m]**2). Ethnicity will be presented as three categories: Hispanic or Latino; Not Hispanic or Latino; Missing.

Disease history and characteristics will include type of myelofibrosis, time since diagnosis, IWG risk level at screening, prior use of hydroxyurea, prior use MF medication, prior splenic radiotherapy, [REDACTED], palpable spleen size below costal margin, [REDACTED], qualifying platelet count, last pre-dose (baseline) platelet count, baseline hemoglobin, and baseline Absolute Neutrophil Count (ANC). Qualifying platelet baseline count is defined as the platelet count at any 4 assessments (at screening, at screening re-test, at the planned day of first study treatment or at its re-test) within qualifying interval for a stratum, i.e. for stratum 1, qualifying platelet count is the last assessment prior to or on the first INC dose date within $[75 - 100] \times 10^9 / L$, for stratum 2 is the last assessment prior to or on the first INC dose date within $[50 - 75] \times 10^9 / L$.

Demographics and other baseline data will be summarized descriptively by stratum and by group for the FAS.

Relevant medical history will be summarized by SOC and PT by stratum and by dose for the FAS

2.2.2 Study treatment

Study treatment data will be summarized descriptively by stratum and group using the Safety Set.

The duration of exposure will be summarized by length of exposure, as well as by duration category (none, < 4 weeks, 4 – < 8 weeks, 8 – < 12 weeks, 12 – < 16 weeks, 16 – < 20 weeks, 20 – < 24 weeks, 24 – < 36 weeks, 36 – < 48 weeks, 48 – < 60 weeks etc).

The following algorithm will be used to calculate the duration of study treatment exposure.

Duration of exposure (days) = [(date of last administration of study treatment) – (date of first administration of study treatment) + 1].

The duration includes the periods of temporary interruption.

Study dose

Cumulative dose is defined as the total dose given during the study treatment exposure. For patients who did not take any drug, the cumulative dose is by definition equal to zero. The total dose taken will be calculated based on INC424 DOSE eCRF page. Dose intensity (DI) is defined as:

$$DI \text{ (mg/day)} = \text{Cumulative dose (mg)} / \text{Duration of exposure (days)}$$

Relative dose intensity (RDI) for the first cycle of treatment is defined as:

$$RDI \text{ (\%)} = (\text{Cumulative dose over first cycle}) / (\text{Total planned starting dose over first cycle}) \times 100\%$$

where total planned starting dose as Duration of treatment (days) * starting dose of the assigned cohort.

The summaries of cumulative dose, DI and RDI will be presented.

A dose reduction is defined as a reduction of the total daily dose to a non-zero dose of one day or greater. A dose interruption is defined as a total daily dose of 0 mg for a duration of one day or greater.

The number (%) of subjects who had a dose interruption or dose reduction will also be summarized.

The dosing information will be listed by stratum, dose level and patient.

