### 5.1.2.7 Intra-patient escalation

Intra-patient dose escalation will only be permitted after Study Day 56. During the course of the study, patients can be dose-escalated to the next higher dose level only once every two cycles (each cycle is 28 days), provided that ALL of the following criteria are met:

- inadequate efficacy is seen with the current dose level, as defined by observation of one or both of the following:
  - not achieving at least a 50% reduction in palpable spleen length compared to Study Day 1
  - lack of meaningful improvement in disease symptoms based on the Investigator's expert judgment.
- no treatment-related toxicity has occurred with the current dose level, resulting in treatment reduction or interruption or discontinuation in the previous 56 days.

For the first 24 weeks of treatment for an individual patient, the dose-escalation requirements will be as follows:

- the maximum dose with which the patient is to be treated does not exceed 15 mg b.i.d. and has been evaluated with at least 3 patients for a minimum of 28 days in that stratum, with no more than 1 out of 3 patients experiencing DLT
- the minimum PLT count during the first 24 weeks period is  $\geq 50 \times 10^9/L$  OR  $\geq 75\%$  of the baseline PLT count the current dose level is lower than the MSSD.

For treatment beyond the first 24 weeks, the dose-escalation requirements will be as follows:

- the maximum dose with which the patient is to be treated is the higher of: the MSSD established for that stratum OR 10 mg bid
- the minimum PLT count at the time of the escalation is  $\geq 50 \times 10^9/L$  AND is  $\geq 75\%$  of the baseline PLT count if a patient experienced a PLT count  $\leq 50 \times 10^9/L$  OR  $\leq 75\%$  of the baseline PLT count beyond the first 24 weeks, a dose escalation may be discussed with the sponsor. If a patient experiences a second episode of PLT count  $\leq 50 \times 10^9/L$  or  $\leq 75\%$  of the baseline PLT count (if it is suspected to be drug related), no further dose escalation will be allowed.

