### 5.2.4 Drug compliance and accountability

#### 5.2.4.1 Drug compliance

Compliance with the INC424 regimen will be calculated by the Sponsors based on the drug accountability documented by the site staff and the review of the paper treatment-compliance diary completed by the patient and will be monitored by the Sponsors/designee (pill counts in accordance with the relevant Standard Operating Procedures). A patient will be considered sufficiently compliant with INC424 treatment if they have taken at least 83.3% of their prescribed dose over the total duration of study drug dosing.

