## **9.3 Treatments (study drug, concomitant therapies, compliance)**

The dose and duration of INC424 will be listed and summarized by dose level using descriptive statistics. Data may be presented by cycle in addition to over the entire study duration. The daily dose will be summarized using descriptive statistics by dose level and will be listed by patient.

Concomitant medications and significant non-drug therapies prior to and after the start of the study drug will be summarized for the safety set.

Compliance to the study protocol will be assessed by reporting the number and type of protocol deviations. These will be identified prior to database lock and will be listed and summarized. Compliance to study drug, for the period from Study Day 1 to end of treatment, will be summarized by categories of < 83.3% vs. ≥ 83.3% and will be reported by dose level or combination of dose levels as appropriate.

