2.2.5 Compliance

Compliance to the study protocol will be assessed by reporting the number and type of CSR reportable protocol deviations. These will be identified in the VAP document for Protocol Deviation prior to database lock and will be listed and summarized. Compliance to study drug, for the period from Study Day 1 to end of first cycle, i.e. RDI for the first cycle of treatment will be summarized by categories of < 83.3% vs. ≥ 83.3% and will be reported by dose level.

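### SAP 2.2.5 replaces the protocol's compliance measure with first-cycle relative dose intensity against the starting dose, without announcing the change, and leaves that measure's denominator undefined

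*SAP*

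**What the plan says.** **Protocol.** Section 5.2.4.1 calls a patient sufficiently compliant on taking "at least 83.3% of their prescribed dose over the total duration of study drug dosing". Section 9.3 sets the reporting period: "Compliance to study drug, for the period from Study Day 1 to end of treatment", split at 83.3%. The denominator is the prescribed dose and the period is the whole of treatment.

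**SAP.** Section 2.2.5 reports compliance "for the period from Study Day 1 to end of first cycle, i.e. RDI for the first cycle of treatment", split at the same 83.3%. Section 2.2.2 supplies the measure: "Relative dose intensity (RDI) for the first cycle of treatment is defined as" the cumulative dose over the first cycle divided by a quantity labelled as the total planned starting dose over that cycle. The explanatory line then reads "where total planned starting dose as Duration of treatment (days) * starting dose of the assigned cohort".

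Duration of treatment is not defined. The one duration that section 2.2.2 does define is exposure: "Duration of exposure (days) = [(date of last administration of study treatment) – (date of first administration of study treatment) + 1", with the note that "The duration includes the periods of temporary interruption". That definition has no cap at the end of cycle 1.

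SAP section 2 says the data will be analysed according to section 9 of the protocol. Where the SAP alters the definition of the dose-determining set (DDS), section 2.1.1 says so and gives the reason. Section 2.2.5 carries no such note.

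**The concern.** Two things change between protocol and SAP while the word compliance and the 83.3% threshold stay the same: the denominator (starting dose instead of prescribed dose) and the period (cycle 1 instead of all treatment).

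The first change matters because the protocol itself can take the prescribed dose below the starting dose within cycle 1. Section 5.1.2.8 interrupts therapy after a DLT. Table 5-6 limits the restart dose after grade 4 thrombocytopenia or neutropenia. For days 1 to 28, Table 5-4 also requires holds for some toxicities that are not treatment-related, followed by resumption at the same dose. A patient who follows these instructions exactly can land in the category that the protocol uses for insufficient compliance.

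The second change removes all treatment after cycle 1 from the compliance table, in a study planned to treat for up to 3 years.

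Separately, the RDI label and its explanatory line can be programmed in more than one way. At stake is whether the first-cycle dose-intensity and compliance tables mean what their titles say.

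**Working it through.** The documents give no worked RDI value, so there is no stated figure to reproduce. The check applies the two definitions to simple dosing patterns.

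**Inputs**
- Cycle length: "each cycle is 28 days" (protocol 5.1.2.7). With twice-daily dosing this is 56 doses.
- Cut-off: 83.3% (protocol 5.2.4.1 and 9.3; SAP 2.2.5).
- Starting total daily doses: 10, 15, 20, 25 and 30 mg (protocol Table 5-2).
- Restart after a hold: at most 5 mg b.i.d., i.e. 10 mg/day, for at least 2 weeks (protocol Table 5-6, highest platelet or ANC row).

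**Formulas**
- SAP: RDI = dose taken in cycle 1 / (D × starting daily dose), where D is the duration of treatment.
- Protocol: compliance = dose taken / dose prescribed.

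**1. Hold in cycle 1, resumed at the same dose.** For a patient still dosing at Day 28, D = 28 whether it is fixed or capped. A hold of h days gives (28 − h)/28.
- 1 to 4 days: 96.4%, 92.9%, 89.3%, 85.7%. All are above the cut-off.
- 5 days: 23/28 = 82.1%. 7 days: 21/28 = 75.0%. Both are below.
- In doses: 9 of 56 missed gives 47/56 = 83.9%; 10 of 56 missed gives 46/56 = 82.1%.

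**2. Hold with a reduced restart.** Take a 3-day hold from Day 15, then 10 mg/day for the remaining 11 days.
- Start 30 mg/day: (14×30 + 11×10)/(28×30) = 530/840 = 63.1%
- Start 25: 460/700 = 65.7%
- Start 20: 390/560 = 69.6%
- Start 15: 320/420 = 76.2%
- Start 10: 250/280 = 89.3%

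Four of the five starting doses fall below 83.3%. On the protocol's measure, with nothing prescribed during the hold, each of these patients scores 100% (530/530 for the first). The protocol does not say how hold days enter the prescribed dose. If they were counted at the starting dose, the first patient would score 530/(530 + 3×30) = 530/620 = 85.5% over cycle 1, still above the cut-off. Under that alternative the 5-day same-dose hold would be 82.1% on both measures, so step 1 depends on the assumption and this 30 mg/day example does not.

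**3. Early stop, D capped at Day 28.** A patient who takes every dose and stops on Day 10 has D = 10 and RDI = 10/10 = 100%. Against the planned cycle the figure is 10/28 = 35.7%. A patient held from Day 15 who never resumes has D = 14 and RDI = 14/14 = 100%, against 14/28 = 50.0%. On this reading the patient who could not resume scores 100%, and the one in step 2 who did resume scores 63.1%.

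**4. Period.** Planned treatment to Week 156 is 156 × 7 = 1,092 days. The SAP's compliance table covers the first 28.

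**The case against.** The case against making much of this is substantial, and most of it stands.

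- **The primary result is untouched.** A reader might infer that this table is the exposure evidence behind the DLT result. The documents give it no such role. DDS membership has its own rule (more than 20% of planned doses or more than 6 consecutive doses missed), and SAP 2.1.1 keeps every patient with a DLT. The model in SAP 2.3.1 uses dose, stratum and DLT status.
- **Early stoppers are not hidden.** SAP 2.2.2 has an exposure category below 4 weeks, counts of interruptions and reductions, and dosing listings. SAP 2.3.2 tabulates DLTs, AEs leading to discontinuation and AEs requiring dose adjustment or interruption.
- **The early stopper's 100% is not wrong as compliance.** Dose taken against dose prescribed also gives 100%. The score is misleading only as first-cycle dose intensity, and it requires full dosing up to the stop.
- **Not every required hold is penalised.** Holds of 4 days or fewer with same-dose resumption stay above the cut-off.
- **The whole-study reading of duration is strained.** Inserting the defined exposure duration would give a fully adherent patient 28/34 = 82.4% at 34 days and 28/1,092 = 2.6% at Week 156. A reader might infer that the SAP would produce this, but the denominator's own label limits it to the first cycle.
- **A fixed 28 days is also a possible reading.** It fits the label, and the early-stop point then disappears. It does not remove the hold and restart results in steps 1 and 2.
- **The substitution is visible.** SAP 2.2.5 names RDI openly, so a careful reader of the table would know what was computed.

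Visibility does not answer the main point. The SAP says it follows protocol section 9, keeps that section's term and threshold, and reports a different quantity over a different period.

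**Conclusion.** The point holds for the descriptive tables and no further. SAP 2.2.5 does not report the compliance that protocol 5.2.4.1 and 9.3 define, and does not acknowledge the difference. Fully adherent patients can be placed below 83.3%: from 5 hold days with same-dose resumption, and at 63.1% in the 30 mg/day example. Compliance after cycle 1 is not reported at all. The first-cycle RDI denominator is ambiguous; the early-stop discrepancy of 100% against 36% arises only if duration is capped at Day 28.

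The size rests on whole-day holds, otherwise complete dosing, nothing prescribed during a required hold, and, in the restart example, recovery that permits 10 mg/day after 3 days. The documents do not say how many patients follow these patterns, so the number misclassified cannot be estimated. DLT rates, the DDS, the Bayesian model and the MSSD are unaffected. It should be corrected because the tables would otherwise carry the wrong meaning, and correction is cheap.

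**What to change.** 1. In SAP 2.2.5, define compliance as dose taken divided by dose prescribed after permitted modifications, from Day 1 to end of treatment, with the 83.3% split, as protocol 5.2.4.1 and 9.3 state. Say explicitly that the prescribed dose is zero during a required hold.
2. In SAP 2.2.2, set the first-cycle RDI denominator to 28 days × planned total daily starting dose for every patient. Present it as dose intensity, not compliance, and show patients who stop before Day 28 separately so that early stopping is not mixed with reduced dosing.
3. If a first-cycle compliance figure is still wanted, add it alongside and note the departure from the protocol, as section 2.1.1 does for the DDS.

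The cost is a few lines of SAP text and revised derivations. Protocol 5.1 already requires prescribed doses and dose changes on the eCRF, and Tables 6-1 and 6-2 list drug accountability as database data. No new data collection and no change to any dosing rule is involved.
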